6.3 MEASURES TO MINIMIZE BIAS: RANDOMIZATION AND BLINDING

This study will be a double-blinded randomized controlled placebo trial.

To avoid selection bias, eligible participants will be randomly allocated in 1:1 ratio, to either oral intake of KE drink or Placebo, using a computer based random sequence generation method which will be concealed. Randomization will be stratified by age. There will be 2 groups defined as participants age 55-64 and participants ≥ 65 years old. The formulation of KE drinks and Placebo will be done in a way that does not allow participants to find out in which group they are assigned to. Efforts to match the Placebo with KE drinks are described in 6.2.3.

Unintentional break of the blinding of participants will be reported to the IRB as a study deviation.

Credibility expectancy questionnaire (CEQ):

To assess subjects expectations and confirm their blind status, we modified the CEQ, a tool commonly used in studies of chronic pain and anxiety syndromes [54-56](#). The CEQ will be administered on Visits 3 and 4 (i.e., while participants are receiving the study supplement). It has been shown that expectations can alter the outcome of a therapy in diverse populations and conditions, such as Vietnam veterans, social phobia and generalized anxiety disorder; thus, the CEQ is a valuable questionnaire to exclude that any therapy outcomes are explained by expectations. In our study, participants do not have a disease or cognitive impairment. Nevertheless, cognitive performance, an important exploratory outcome, will be assessed and it is conceivable that it may be affected by expectations. Therefore, responses will be compared between groups and may be used as covariate in sensitivity analyses for cognitive outcomes.

The questions that will be asked are:

- “At this point, how effective do you think the supplement you are receiving will be in changing your brain chemistry and improving your cognitive function”
- “How confident would you be in recommending the supplement to a friend who wishes to change her/his brain chemistry and improve her/his cognitive function”
- “By the end of the 28-day period, how much change in your brain chemistry and improvement in your cognitive function do you think will occur”?
- “At this point, how much do you really feel that the supplement you are receiving will help you to change your brain chemistry and improve your cognitive function”

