7.2 PARTICIPANT DISCONTINUATION/WITHDRAWAL FROM THE STUDY

Participants are free to withdraw from participation in the study at any time upon request.

The PI may discontinue a participant from the study for the following reasons:

- Screen failure.
- The participant meets an exclusion criterion (either newly developed or not previously recognized) that precludes further study participation
- The participant has an adverse event (AE), including clinical signs and/or symptoms, laboratory abnormality, or other medical condition or situation, such that continued participation in the study would not be in the best interest of the participant, at the judgment of the PI.
- The participant manifests significant study non-compliance (e.g. the participant was deemed eligible but didn't show for any Visit. Also, if the participant's log of supplement intake during Visit 3 shows multiple skipped doses or skipped days of intervention).
- The participant has any condition, which in the opinion of the PI, could interfere with the study procedures.
- MRI will be stopped at the request of the participant as a result of claustrophobia or problems associated with lying in the scanner for any length of time. If MRS measures for BHB (primary outcome) cannot be obtained, this will constitute discontinuation of the participation.
- Death.

Participants that are discontinued/withdrawn from the study will be replaced by new participants. The reason for participant discontinuation or withdrawal from the study will be recorded on the medical record.

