9.2 SAMPLE SIZE DETERMINATION

The sample size in this study ($n = 50$ for complete data, 25 receiving KE drinks and 25 receiving placebo) gives the ability to detect an effect size (d) of 0.80 at a two-tailed Alpha of 0.05 and a Power of .80. In other concurrent studies, our ketone-sensitive PRESS sequence is capable of detecting an effect size (d) 0.72, roughly equivalent to an 18% change in BHB to creatine ratio. Since we know that brain ketone uptake is proportional to plasma ketones [15](#), we expect that brain BHB levels will change comparably to plasma BHB levels. A prior study using plasma measurements following KE administration versus placebo showed an effect size (d) of 4.05 [32](#), suggesting more than adequate power for detecting brain BHB changes.

Also, in a previous study (Evans et al) [72](#), 8 healthy young male athletes were tested on a domain of cognitive performance (executive function) before and after a period during which they were taking a ketone supplement (similar but not identical to the KE of the present study) while exercising [72](#). This intervention resulted in peripheral BHB of ~ 1.5 to 2.6 mM (less than the level of peripheral BHB elevation we expect with the KE) and showed a significantly better executive function performance, with an effect size (d) of 0.7 [72](#). Since in our proposed study we expect to achieve a greater peripheral BHB induction and our sample size is much greater than Evans et al [72](#), it is likely that our study is powered well enough to detect cognitive changes.

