9.4.2 Analysis of the Primary Endpoints

The primary endpoint will be continuous and will be presented as mean (standard deviation). It will be measured as MRS BHB concentration normalized to Creatine (BHB/Creatine ratio) in bilateral precuneus. For the primary endpoint, repeated-measures mixed models analysis will be performed to examine the effects of the between-subjects factor “Group” (KE drink vs. Placebo group), the within-subjects factor “Time” and their Interaction, separately for acute and chronic effects (Baseline vs. Outcome). Exploratory analyses will include age, sex, weight/BMI, waist circumference, TGs, glucose levels, HDL levels, Blood Pressure levels (reflecting severity of MetS), cognitive status, peripheral ketone levels and EV biomarkers, entered as covariates in the mixed model. If a covariate is not substantively related to the model ($p > 0.15$), it will be dropped.

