9.4.9 Exploratory Analyses

All analyses related to serum BHB, EV biomarkers, cognitive performance, thigh MRS and stool microbiome will be exploratory. Also, exploratory analyses will be performed for the primary endpoint to include additional covariates to the mixed model.

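### As written, the covariate-adjusted analyses of brain BHB either leave the Group × Time result unchanged by construction or adjust for variables the treatment may have altered

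*Protocol*

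**What the plan says.** Protocol 9.4.2 states that "repeated-measures mixed models analysis will be performed to examine the effects of the between-subjects factor" Group, together with Time and their interaction. Acute and chronic effects are modelled separately, each as baseline against outcome. I therefore take each model to have two occasions per person.

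The same paragraph lists age, sex, weight/BMI, waist, triglycerides, glucose, HDL, blood pressure, cognitive status, peripheral ketones and EV biomarkers for exploratory analyses, "entered as covariates in the mixed model. If a covariate is not substantively related to the model", after which a covariate with p > 0.15 is removed. Section 9.4.9 adds that "exploratory analyses will be performed for the primary endpoint to include additional covariates to the mixed model". The SAP repeats both statements.

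Three things are left open: whether a covariate × Time term is included, which p-value the 0.15 rule reads, and whether re-measured covariates enter as baseline or visit-specific values. Section 9.4.3, by contrast, does write out interactions with Group and Time for genotype.

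**The concern.** The treatment question in this model is Group × Time, the difference between arms in within-person change. A main-effect covariate with one value per person shifts both scans equally, so it has no way to act on that contrast.

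An adjusted result identical to the unadjusted one would then be a property of the model, yet in a report it could be taken as showing that the finding survives adjustment for metabolic syndrome severity or baseline imbalance. The analysis would also gain no precision from covariates that predict response, and the retention rule could discard those covariates.

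If re-measured variables are instead entered by visit, the estimate can move, but part of what moves it may be an effect of treatment. Peripheral ketones are the clearest case.

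**Working it through.** **1. The plan's own figure.** Inputs from Protocol 9.2 and 6.3: "the ability to detect an effect size (d) of 0.80", "two-tailed Alpha of 0.05 and a Power of .80", "25 receiving KE drinks and 25 receiving placebo", and "eligible participants will be randomly allocated in 1:1 ratio".

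n per arm = 2(1.960 + 0.842)² / 0.80² = 2 × 7.85 / 0.64 = 24.5, so 25. Power at 25 per arm is 0.807 by the normal approximation and 0.791 by the t-test (which needs 25.5 per arm). The stated figure reproduces, and it concerns the unadjusted comparison.

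**2. Algebra.** For person i with arm g and one-value covariate x:

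- baseline scan: y₁ = a + b·g + γ·x + e₁
- outcome scan: y₂ = a + τ + (b + δ)·g + γ·x + e₂
- change: y₂ − y₁ = τ + δ·g + (e₂ − e₁)

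δ is Group × Time, and γ·x has gone. With complete pairs, δ is estimated by the difference in mean change, with SE = s_change × √(1/25 + 1/25), whether or not x is in the model. If x also interacts with Time, its slopes are γ₁ and γ₂, the change contains (γ₂ − γ₁)·x, and adjustment acts on δ.

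**3. Numerical check.** Single simulated trials, 25 per arm, REML. Assumed, because the documents give no raw SD, scan correlation or covariate strength: residual SD 1, correlation 0.5, effect 0.8. Entries are Group × Time (SE).

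| Covariance; covariate slopes at baseline/outcome | No covariate | Main effect | With covariate × Time |
|---|---|---|---|
| Random intercept; 0.6/0.6 | 0.963 (0.2268) | 0.963 (0.2268) | 0.952 (0.2263) |
| Unstructured; 0.6/0.6 | 0.901 (0.2685) | 0.901 (0.2685) | 0.893 (0.2692) |
| Unstructured; 0.2/1.2, outcome SD 1.6 | 0.285 (0.4754) | 0.285 (0.4754) | 0.623 (0.4555) |

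In the last row, regressing the change on arm and covariate also gives 0.623 (0.4555).

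**4. The p > 0.15 rule.** 400 simulated trials per scenario, same assumptions. A main-effect p-value tests the average slope, (γ₁ + γ₂)/2. The treatment contrast depends on γ₂ − γ₁.

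| Slopes | Kept, tested on level | Kept, tested on change | Mean SE, unadjusted to change-adjusted |
|---|---|---|---|
| 0.6/0.6 (level only) | 99.8% | 15.3% | 0.281 to 0.284 |
| −0.3/0.3 (change only) | 15.5% | 99.3% | 0.329 to 0.286 |
| 0/0.6 (outcome only) | 82.3% | 99.0% | 0.326 to 0.282 |
| 0/0 (unrelated) | 14.5% | 18.5% | 0.280 to 0.283 |

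In the second row adjustment would cut the SE by 1 − 0.286/0.329 = 13%, yet the level screen keeps the covariate at about the chance rate. In the first row it almost always keeps a covariate that gains nothing.

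**5. Where the cancellation fails.**

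- *Covariate entered by visit.* A constructed ketone-like covariate, raised strongly by treatment at outcome, moved Group × Time from 0.963 to −1.504 (SE 0.420). A re-measured covariate unaffected by arm (assumed slope 0.4, visit correlation 0.7, 150 trials) moved it by 0.067 on average, 95th percentile 0.16, against a true 0.8.
- *Incomplete pairs.* With 8 of 50 outcome scans missing, adding the main effect moved the estimate from 0.889 to 0.928 (unstructured) and 0.916 to 0.949 (random intercept). In the unequal-variance data it moved from 0.145 to 0.158 and from 0.177 to 0.233.
- *The Group term.* It changed from −0.012 (SE 0.304) to 0.035 (SE 0.265). With Time coded 0/1 this is the baseline difference between arms, not the treatment effect.

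**The case against.** A reader might infer that the adjusted analysis can never change the treatment result. The documents do not support that. The covariate list ends with peripheral ketones and EV biomarkers, which Protocol 8.3 has measured at Visits 2, 3 and 4. Weight, waist and laboratory values recur at Visit 4, vital signs at every visit, and cognition at Visits 2 and 4. Only age and sex are fixed by nature, and 9.4.2 does not say that any covariate is a baseline value. The modified intention-to-treat set can also hold people with a baseline scan only. Protocol 7.2 limits this ("Participants that are discontinued/withdrawn from the study will be replaced by new participants"), as does the evaluability rule in 9.3.2, but neither excludes it.

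Main-effect entry is itself an inference. Section 9.4.3 spells out interactions for genotype because effect modification is the question there, so the contrast is suggestive rather than conclusive. Likewise the 0.15 rule names no term, so screening on the wrong association follows only if the rule reads the main-effect p-value. The 15.5% retention needs slopes of opposite sign at the two scans; in the less contrived outcome-only case it is 82%.

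Finally, the documents call these analyses exploratory and nowhere present them as a robustness check.

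All of this stands and limits the claim. It does not rescue the adjustment: time-fixed main effects do nothing to Group × Time with complete pairs, by-visit entry conditions on possible consequences of treatment, and the text does not say which is meant.

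**Conclusion.** The point holds for covariates with one value per person, entered as main effects, with complete pairs. Group × Time and its SE are then exactly unchanged. This is algebra and needs none of the simulation inputs. On the same reading, the p > 0.15 rule selects on average BHB/creatine. For re-measured covariates entered by visit the problem differs: the estimate can move, but it is no longer a clean adjusted treatment effect.

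The consequence is limited to exploratory analyses. A reader might infer a power shortfall from a further simulation, in which unadjusted power was 64–70% against 78–79% with covariate × Time. That would be wrong. There the effect was 0.8 of the residual SD, and a covariate explaining 20–30% of the change enlarges the total SD, so the standardised effect falls to 0.8 × √0.80 = 0.716 or 0.8 × √0.70 = 0.669. The plan's d = 0.80 is not stated on that scale, and its sample size reproduces. The power, retention and SE figures are illustrative only.

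The plan should be changed because the remedy is cheap and makes the adjusted comparison informative.

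**What to change.** In Protocol 9.4.2 and the matching SAP section:

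- For the adjusted treatment comparison, use only values measured before the first dose, and enter each with its interaction with Time. With complete pairs this equals regressing the change on arm and covariate. Regressing the outcome scan on arm, baseline scan and covariate answers the same treatment question, though it need not give the same number; name one form.
- Replace the p > 0.15 screen with a short list fixed in advance by the sponsor, including the age stratification factor (55–64, ≥ 65).
- Report Group × Time with its 95% CI before and after adjustment.
- Report models containing post-dose ketone or EV values separately, as association or mediation analyses, not as adjusted treatment effects.

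Cost: a few sentences in each document and a few model degrees of freedom out of 50 participants, which is the reason to keep the list short. No new data are needed, and the unadjusted primary analysis stays as it is.

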9.4.3 Analysis of the Secondary Endpoint(s)

To assess whether genetic factors modulate the response to the KE supplement, in the repeated-measures mixed models, we will include the *APOE* $\epsilon 4$ carrier status ($\epsilon 4$ carriers, $\epsilon 4$ non-carriers), the *SLC16A7*, and potentially other polymorphisms, as additional fixed effect factors and their interactions with “Group” and “Time”.

9.4.4 Safety Analyses

The study will not evaluate safety endpoints formally. However, AEs will be published at the time of the final research report and will be analyzed as summary statistics. We will report AEs as incidence per administration of total doses of KE drink vs Placebo. Also, we will report AEs as number of participants with a specific AE per group. In case of an AE presenting with different severities, we will subcategorize incidence based on the severity group.

9.4.5 Baseline Descriptive Statistics

We will present baseline characteristics including demographics, clinical labs, and anthropometric characteristics (age, sex, ethnicity, BMI, weight, waist circumference, TGs, glucose levels, HDL levels, Blood Pressure levels, cognitive status, peripheral and brain ketone levels (BHB, AcAc), EV biomarker levels) using descriptive statistics. Inferential statistics will not be used.

9.4.6 Planned Interim Analysis

N/A

9.4.7 Sub-Group Analyses

We may perform exploratory subgroup analyses based on age groups, sex, ethnicity, baseline cognitive status or other factors, especially if there are baseline differences. We may also perform exploratory sensitivity analyses using the responses of the credibility expectancy questionnaire as covariate to assess any effects of subjective expectations.

9.4.8 Tabulation of individual Participant Data

Individual participant data will be listed by measure and time point.

9.4.9 Exploratory Analyses

All analyses related to serum BHB, EV biomarkers, cognitive performance, thigh MRS and stool microbiome will be exploratory. Also, exploratory analyses will be performed for the primary endpoint to include additional covariates to the mixed model.

10 REGULATORY AND OPERATIONAL CONSIDERATIONS

10.1 INFORMED CONSENT PROCESS

10.1.1 Consent/Assent Procedures and Documentation

The consent will be obtained in person at the NIA Clinical Unit. The PI, clinical research coordinator (nurse), associate investigators, and NIA research nurses and nurse practitioners will be authorized to obtain consent.

All participants will receive a verbal explanation in terms suited to their comprehension of the purposes, procedures and potential risk of the study and of their rights as research participants. Participants will have the opportunity to carefully review the written consent form and ask questions regarding this study prior to signing.

When the participant fully understands her responsibilities and possible risks and discomforts and agrees to participate in the current study, they will be provided with the consent to sign. A signed copy will be provided to each participant, as well as placed in her medical record. No procedures will begin until the informed consent has been properly obtained.

In particular, the summary study design will be detailed. Furthermore, participants will be fully informed about the data and safety monitoring procedures.

The informed consent procedure might last up to an hour according to our previous experience, allowing for thorough explanation of the study's procedures and answer of possible questions. The clinical research coordinator (nurse) and the PI will be available to answer any question that participants may have. Participants can have additional time to think and decide on their participation. Additionally, they will have the option to discuss with their families and/or friends and/or primary physician before they provide consent.

When an NIH staff member in our work unit seeks to enroll in the study, a consent monitor who is independent of the research team will be present to observe the consent process. Conversely, we will contact the CC Department of Bioethics Consultation Service or the NIMH Human Subjects Protection Unit (HSPU) in order to enlist a consent monitor who can observe remotely. If no such person is available, consent observation will be performed by another qualified investigator on the study other than the staff member's supervisor.

10.1.2 Participation of Subjects who are/become Decisionally Impaired

Adults unable to give consent are excluded from enrolling in the protocol. If during study, a previously eligible participant becomes decisionally impaired she/he will be withdrawn from the study.

10.2 STUDY DISCONTINUATION AND CLOSURE

This study may be temporarily suspended or prematurely terminated if there is sufficient reasonable cause. If the study is prematurely terminated or suspended, the PI will promptly inform study participants and the IRB and will provide the reason(s) for the termination or suspension. Study participants will be contacted, as applicable, and be informed of changes to study visit schedule.

Circumstances that may warrant termination or suspension include, but are not limited to:

- Determination of unexpected, significant, or unacceptable risk to participants
- Insufficient compliance to protocol requirements
- Data that are not sufficiently complete and/or evaluable

Study may resume once concerns about safety, protocol compliance, and data quality are addressed, and satisfy the IRB and/or Food and Drug Administration (FDA).

10.3 CONFIDENTIALITY AND PRIVACY

Participant confidentiality and privacy is strictly held in trust by the participating investigators and their staff. This confidentiality is extended to cover testing of biological samples in addition to the clinical information relating to participants. Therefore, the study protocol, documentation, data, and all other information generated will be held in strict confidence.

All research activities will be conducted in as private a setting as possible.

Identifiers will be attached to medical records and to data stored in password-protected computers and servers but not to samples. All samples will be coded and the link of these codes will be available to the PI and other investigators. Access to the “key” for the code will be limited to investigators in this study. Data or samples may be shared with other researchers at the PI’s lab and other NIH investigators to conduct biomarker measurements, but the “key” will not be shared with them. Personally identifiable information will not be released to third parties, unless required by law (specifically, HIV, HBV, HCV results).

The study monitor (NIA Clinical Director or designee), representatives of the Institutional Review Board (IRB), and/or regulatory agencies may inspect all documents and records required to be maintained by the investigator, including but not limited to, medical records (office, clinic, or hospital) and pharmacy records for the participants in this study. The clinical study site will permit access to such records.

The study participant’s contact information will be securely stored at each clinical site for internal use during the study. At the end of the study, all records will continue to be kept in a secure location for as long a period as dictated by the reviewing IRB or Institutional policies requirements.

Study participant research data, which is for purposes of statistical analysis and scientific reporting, will be transmitted to and stored at NIA-approved servers and software platforms that grant limited access to study PI and designees and are secure and password-protected. The participant’s contact or identifying information will only be stored in the medical record and NIA-approved clinical application electronic platform. In servers containing research data, individual participants and their research data will be identified by a unique study identification number.

To further protect the privacy of study participants, a Certificate of Confidentiality has been issued by the National Institutes of Health (NIH). This certificate protects identifiable research information from forced disclosure. It allows the investigator and others who have access to research records to refuse to disclose identifying information on research participation in any civil, criminal, administrative, legislative, or other proceeding, whether at the federal, state, or local level. By protecting researchers and institutions from being compelled to disclose information that would identify research participants, Certificates of Confidentiality help achieve the research objectives and promote participation in studies by helping assure confidentiality and privacy to participants.

